## **Recruitment**

Each of the three types of recruitment and retention efforts is described below:

*Sponsoring Organizations.* We seek to recruit 3 organizations for our Aim 2 activities and 6 organizations for our Aim 3 activities; the Aim 2 organizations will be able to continue as Aim 3 organizations. Since these sponsoring organization leaders will be involved in the Aim 2 and 3 studies, we will seek their informed consent for participation in the studies. We are specifically seeking to recruit organizations serving the targeted minority groups, as well as those serving a more mixed or majority clientele. Several of the study team members and program advisors are either directly involved with or have strong contacts with potential sponsoring organizations, and we have already identified preliminary organizational interest in taking part in the project. Beyond those specific contacts, the project Co-PIs, [name] and [name], can draw on their extensive networks for organizational recruitment. Past experience with organizations that have adopted Savvy testifies to the long-lasting involvement with the program: once adopted, Savvy remains a regular part of the organization's portfolio, so we do not expect organizational retention to prove a problem. Procedures in our Aim 2 and 3 approach involve considerable interaction between the project team and sponsor organization leadership, including the provision of information and feedback that can help these organizations to improved Savvy uptake among their clients. This interaction will also promote retention in the project.

*Interventionists.* It will be the sponsoring organizations who will identify individuals – from their existing staff or from volunteers whom they recruit – to be trained as Savvy interventionists by the system we develop and to lead Savvy programs that the sponsors organize. Guided by orientation and administrative materials and protocols that we will provide, the sponsors will organize the training, organize the Savvy programs, and conduct regular debriefings with the interventionists. Since these interventionists will be involved in the Aim 2 and 3 studies, we will seek their informed consent for participation in the studies. In

addition to sponsor-based debriefings, the semi-structured interviews we will conduct with the interventionists during the Aim 2 and Aim 3 studies will also provide a linkage for them to the overall study and will, hopefully, provide them with a sense of ownership in the developing system.

*Caregivers.* It will only be family caregivers who will be part of the clinical trial component of this study (in Aims 2 and 3). Recruitment into the studies will be through referral from the sponsoring organizations. Each organization will recruit caregivers to take part in Savvy programs provided by interventionists trained in the system we are developing. We will provide organizations with materials they can use to announce Savvy and the studies; we will encourage the organizations to insert these materials into their own standard informational templates (i.e., standard logo and graphics). For caregivers willing to do so, their contact information will be provided to the Emory study team. We will arrange a phone or video call with each during which we will explain the study (Aim 2 or Aim 3 – a caregiver will not be able to take part in both), explain eligibility criteria, and seek informed consent (verbally) for participation. We do not anticipate attrition to be a problem in the Aim 2 study; research contact, following consent, will occur over a very brief period of time. All who consent to the Aim 2 study will take part immediately in a Savvy program and in an on-line survey and (for some) in-person interview conducted by phone or video right after the program. Prolonged retention will be more of a challenge in the Aim 3 study. Those taking part will enter a Savvy program either immediately or after a delay based on scheduling at the individual agencies. For those taking part immediately a series of 3 phone or video interviews will bracket their Savvy participation (at baseline then at 3 and 6 months following baseline. For those with a delayed start, we will conduct 4 interviews (upon sign up, immediately prior to the start of the program and then 3 and 6 months after program completion). To foster engagement with the project, we will prepare and distribute to participants a monthly project newsletter,

featuring tips on exercise and healthy eating and profiles of the study team. We will also send birthday and seasonal holiday cards, as appropriate.

## **Field Methods**

**Data Collection and Management.** Emory study staff will use an IRB-approved phone or video consent process to enroll individuals from the three groups that are targets for our formative evaluation activities, and study staff and team members will gather data from them in the ways described below:

*Interventionists.* We will conduct three recorded semi-structured video interviews with each interventionist. One will occur immediately after training; this will focus on their sense of the completeness and adequacy of the training program, including the training methods, videos, and materials, and their perceived readiness to lead the program. We will also interview them immediately after the conduct of each of the two Savvy programs they lead, asking them to report on their own performance as interventionists, including any adaptation processes in which they might have engaged, and to reflect on ways the training might be improved to strengthen their skills, including for adaptation. In total: 18 interviews.

*Savvy Participants.* Using an on-line survey method, we will ask each caregiver to complete the post-program fidelity monitoring survey (see Appendix) that seeks responses to the program (feel more knowledgeable, more competent, better equipped, etc.) and asks them to assess the interventionist's performance and verify that certain key elements of the program were covered (N=36; 6 in 6 groups). We will also conduct recorded semi-structured video interviews with a small sample of participants (N=8-12), selected to achieve maximum variability of relationship to care recipients, gender, racial/ethnic heritage, and rating of the program and the interventionists. Interviews will focus on caregivers' perceptions of the interventionist's

program leadership skills, any adaptation experiences, and on ways in which they met their own needs and expectations.

*Organizational Leaders.* We will conduct recorded semi-structured video interviews with sponsoring organizations' key contact persons immediately after the interventionist training and then after each of two Savvy offerings. The conversation will focus on identifying ways to strengthen and improve the training, certification, and fidelity monitoring system. We will also seek information about time and resource costs of the program, caregiver demand, and caregiver recruitment and feedback (3 interviews per organization).

Results from Savvy participant quantitative fidelity monitoring surveys will be compiled in a simple spread sheet to allow us to see whether there are any notable problems in interventionist performance either within or across sites or in or across interventionists. Likewise, we will be able to compare caregivers' responses about knowledgeability and competence with responses we have received from other caregivers in Savvy programs provided by interventionists who were trained in person by [name] or [name].

Once a cohort of 20 consented caregivers has been formed at any local organization, participants will be assigned (through a random procedure administered by Emory staff) to take part immediately in one of the Savvy programs offered by either of the 2 interventionists or to take part in one of the 2 interventionists' programs after 4 months; follow-up phone or video interviews will be conducted at 2, 4, and 6 months lasting each 1-1.5 hours in length. The audio files from interviews will be saved on Emory School of Nursing's secure share-drive within a password protected folder for 5 years post-study completion.

## **Measures**

The table below describes the well-established instruments to be used in caregiver interviews.

Category	Instrument	Instrument Description	Psychometrics
Demographic Information	Demographic sheet Caregiving History	SES, Person living with dementia information, length of caregiving, co-residence with recipient.	Study-developed form (Baseline only)
[Caregiver Vars] Depression	Center for Epidemiological Studies-Depression	A 20 item Likert scale scored 0-3 with somatic and psychological subscales	Alpha=.85; validity well-established 
Anxiety	State-Trait Anxiety Inventory	A 20-item 4-point Likert scale is sensitive to changes in transitory anxiety	STAI state sensitive reliability reported at .94 
Burden	the Zarit Burden Inventory (ZBI),	A 22-item 4-point Likert scale, widely used in caregiving studies	Used in multiple studies with well-established validity 
Caregiver Mastery	Pearlin Mastery, Loss, and Competence	6 brief (3-6 item) Likert scales assessing mastery and loss dimensions	Alpha coefficients from .71-.92. 
Caregiver Skill	Caregiver Assessment of Behavioral Skill	17-item self-report assessment of behavioral management skills	Chronbach alphas from 0.75-0.94 with good validity
[PLWA] BPSD	Revised Memory and Behavior Problem Checklist	22-item Likert scale that assesses patient behaviors and caregiver responses to them	Reliabilities of .84-.90 reported for behavior and reaction. 

## Informed Consent Process

### *Recruitment*

Caregivers in the Aim 2 and 3 studies will learn about the studies from the local organization that is sponsoring Savvy interventionist training and offering the Savvy program to its constituents, using its usual modes and methods of providing information to these constituents. We will provide all collaborating organizations with materials they can use to announce Savvy and the studies; we will encourage the organizations to insert these materials into their own standard informational templates (i.e., standard logo and graphics). These organizations will explain their role in the development project and secure individuals' permission for the Emory study staff to contact them with additional information about the studies; alternately, the announcement materials will provide contact information for the project director at Emory, so individuals can also call directly. Under either scenario, the project will arrange a phone or video conversation with these individuals to assess for study eligibility.

Once eligibility has been established, the project director will provide more information about the components of the relevant study (i.e., Aim 2 or Aim 3). She will allow time for questions, verbally summarizing the material with the subject, and asking subjects to answer a few questions to gauge understanding. For those who remain interested in taking part in the study, we will conduct an IRB-approved phone- or video-based consent procedure. In that procedure, the project director documents, on a pre-established form, that the consent procedure has occurred, the individual has been provided the opportunity to raise questions, has been informed of the voluntary nature of participation and the ability to withdraw from the study without prejudice at any point, and has been told that s/he may continue to raise questions at any point during the study. A copy of the document that the project director signs is then sent to the consenting participant. The original will be retained in a locked cabinet within a locked research room within the School of Nursing. The person will be given information (also on the consent document) about study leadership and how to contact the Project Director, the study Co-PIs, and a neutral informant at Emory.

### *Participant Discontinuation/Withdrawal from the Study*

Participants are free to withdraw from participation in the study at any time upon request. The reason for participant discontinuation or withdrawal from the study will be recorded on the study REDCap. Subjects who receive all or part of the study intervention will not be replaced.

### *Lost to Follow Up*

A caregiver participant will be considered lost to follow-up if he or she fails to complete the scheduled post-intervention follow-up and is unable to be contacted by the study site staff within four weeks of the timepoint.

The following actions must be taken if a participant is determined to be lost to follow-up:

- The research staff will attempt to contact the participant and reschedule the missed appointment for 4 weeks and ascertain if the participant wishes to continue in the study.
- Before a participant is deemed lost to follow-up, the investigator or designee will make every effort to regain contact with the participant (where possible, 3 telephone calls and, if necessary, a certified letter to the participant's last known mailing address or local equivalent methods).
- These contact attempts will be documented in the participant's record in REDCap.

Should the participant continue to be unreachable, he or she will be considered to have withdrawn from the study with a primary reason of lost to follow-up.

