certification and an accompanying performance fidelity monitoring process. This phase will occupy the project's first 14 months and will involve no human subject research participation. Phases 2 and 3 of the study involve human subject research participation. All human subject research activities will be conducted by members of the Emory study team, identified above; no non-Emory study team members will have any contact with Phase 2 and 3 research subjects. The second project phase, which will begin in project month 9 and extend through project month 24, will involve a formative evaluation of the prototype web-based system. In this phase, administrators and interventionists-in-training from 3 collaborating organizations and 36 informal dementia caregivers from these organizations will participate as research subjects. The administrators and interventionists will take part in semi-structured evaluation interviews; the caregivers will be asked to participate in Savvy programs offered by the newly-trained interventionists and they (the caregivers) will be asked to complete pre- and post-Savvy participation interviews both about the effect of the program on them and about their evaluation of the program. Phase 2 results will enable us to revise the interventionist training system, as needed. Once the system is deemed ready, we will, in phase 3, conduct a field test of the system implemented in six culturally and/or organizationally diverse sponsoring agencies. This test will again involve administrators, interventionists-in-training, and 120 dementia caregivers from participating organizations as research participants. The Aim 3 test will principally assess the effectiveness of the system in training interventionists who maintain fidelity to Savvy core principles; this portion of the test involves semi-structured interviews with the administrators, interventionists and a sample of caregivers. The test will also assess the preliminary efficacy of programs led by system-trained interventionists in producing anticipated outcomes in caregiver participants – reduced depression and burden and enhanced caregiving mastery. In this portion of the test, caregivers will be randomly chosen to participate immediately in a Savvy program offered by one of the organization's newly trained interventionists or to participate after a waiting period of 4 months. Those who

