take part in the program immediately will be asked to take part in 3 interviews (baseline and then 3 and 6 months after the start of the program. Those in the delayed start group will be asked to take part in 4 interviews (baseline (at the point of signing up for a later program), immediately prior to the beginning of the program and then 3 and 6 months after the start of the program. Standard instruments will be used to assess burden, mood (anxiety and depression), caregiving confidence and mastery, and care recipient well-being.

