## **10. Plans for analysis**

Multi-level mixed effects models (MLM) with random (participant) and fixed (cohort) effects will be employed to test for linear (and non-linear) trajectories of change for the Intervention group versus waitlist

group focusing on the group-by-time effect. To address the primary effect of the Savvy intervention, the Immediate group will be compared to the waitlist delay group, using the first 2 time points (0m-2m) to test for differences between the 2 groups' changes post intervention. Additionally, the combined Savvy intervention effects will be assessed using a paired t-test for the combined immediate group's first 2 time points (0m-2m) with the waitlist delay group's 2 time points before and after beginning Savvy (4m-6m). If there are significant differences between the 2 groups at the time point immediately prior to receipt of the intervention, these "baseline" effects will be included and adjusted for a final analysis of covariance (ANCOVA) model for these change scores. Given that the immediate group will have 3 post-intervention measurements (2m-4m-6m), MLM longitudinal models will also be employed to assess the overall time effects plus planned post hoc comparisons for both the immediate intervention effect and the longer term and sustained effects. Sidak Type-I error rate adjustment (which has higher power than Bonferroni) will be applied for the multiple pairwise time point comparisons. The proposed study design also has the advantage of capturing "baseline" time points for the delay group (0m-2m-4m) which will provide an excellent opportunity to evaluate what if any potential "placebo" effects there may be from being enrolled in this type of study. These initial data captured at 0m-2m-4m for the delay group will also be used to evaluate any potential decline occurring during this time period. All model assumptions will be tested; grand mean centering used to help combat multi-collinearity between variables; and standard diagnostic tests and influence statistics used to test the distributions of the residuals. MLM models utilize all available data for all participants at each time point and have the advantage of adjusting for the missing data over time, where repeated measures ANOVAs do not. Further covariate predictors of missingness (mainly due to attrition) over time will be included to additionally adjust for these confounders SPSS v.24 will be used for all analyses at the 5% significance level.

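### One unreachable post-intervention interview leads to withdrawal with no provision for later interviews, and during the wait the wording reaches only the immediate arm

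*Combined protocol and SAP*

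**What the plan says.** **The rule (Lost to Follow Up).** The rule covers any caregiver who "fails to complete the scheduled post-intervention follow-up and is unable to be contacted by the study site staff within four weeks of the timepoint". Staff must try to "reschedule the missed appointment for 4 weeks and ascertain if the participant wishes to continue in the study", and must make further efforts: "where possible, 3 telephone calls and, if necessary, a certified letter to the participant's last known mailing address". If these fail, "he or she will be considered to have withdrawn from the study with a primary reason of lost to follow-up". The section does not name the visit that triggers the rule. It does not say whether later interviews are still attempted. It has no rule for a missed interview before the program.

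**The interviews.** Field Methods says that "follow-up phone or video interviews will be conducted at 2, 4, and 6 months", and section 10 uses the same 0, 2, 4 and 6 month points. Section 5 gives the immediate arm interviews at "baseline and then 3 and 6 months after the start of the program", and Recruitment also uses 3 and 6 months. Delayed-arm caregivers are "to participate after a waiting period of 4 months" (section 5).

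**The analysis (section 10).** The primary comparison uses 0 and 2 months. Longitudinal mixed models then address sustained effects, and part of the stated reason for using them is that "MLM models utilize all available data for all participants at each time point".

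**The concern.** Two features of the rule sit badly with the analysis.

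First, it turns a missed visit into a study-level status. Withdrawal in the preceding section is something the participant asks for. Here it is assigned to a caregiver who has asked for nothing and may be reachable again by the next interview. A mixed model can use a caregiver with a gap at one visit, but only if someone collects the later visits.

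Second, the trigger and the mandated tracing are tied to post-intervention visits. Until the delayed arm starts the program it has none. Staff who follow the wording would trace, and if need be withdraw, immediate-arm caregivers, while no rule governs a delayed-arm caregiver who misses an interview over the same months.

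At stake are the number and the balance of observations at the later time points, and the comparability by arm of the retention figures and the completer versus non-completer comparison planned under Data Management.

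**Working it through.** The plan states no dropout rate, effect size or power, so there is no figure of its own to reproduce beyond 6 sponsors × 20 caregivers = 120 (Aim 3), which agrees. No allocation ratio is given; 60 per arm is an assumption.

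**1. Does the label fall before the next interview?** Four weeks = 28 / 30.44 = 0.92 month.

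| Schedule | Missed visit | Label at | Next visit |
|---|---|---|---|
| 2/4/6 months | 2 | 2 + 0.92 = 2.92 | 4 |
| 2/4/6 months | 4 | 4 + 0.92 = 4.92 | 6 |
| 3/6 months | 3 | 3 + 0.92 = 3.92 | 6 |

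It does in every case.

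**2. Whom does the wording reach during the 4-month wait?** Section 10 treats the immediate arm's 2, 4 and 6 month points as post-intervention, and the delayed arm's 0, 2 and 4 month points as baseline. On the 3/6-month schedule the delayed arm's first two interviews (at sign-up and just before the program) are also pre-program. Post-intervention visits inside the wait are therefore 2 and 4 months (or 3 months) in the immediate arm, and none in the delayed arm.

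**3. How many interviews are exposed?** Assume 5–15% of the immediate arm cannot be reached at the first follow-up and that withdrawal ends contact.

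- Caregivers: 0.05 × 60 = 3 to 0.15 × 60 = 9.
- 2/4/6 months: two later visits each, so 6 to 18 of 60 × 2 = 120 interviews. Only the 4-month half, 3 to 9 of 60, belongs to the randomised period.
- 3/6 months: one later visit each, so 3 to 9 of 60, all after the wait has ended.

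If half of these caregivers could be reached again (also an assumption), half of each count is recoverable: 3 to 9 interviews on the first schedule, 1.5 to 4.5 on the second.

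**4. What if unreachability can recur?** Let each visit independently be unreachable with probability m. If the first such visit ends follow-up, the expected count at the k-th follow-up is 60(1 − m)^k. If later visits are still attempted, it is 60(1 − m) at every visit. On the 2/4/6-month schedule:

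| m | Each visit, still attempted | 4 months, rule | 6 months, rule |
|---|---|---|---|
| 5% | 57.0 | 54.1 | 51.4 |
| 10% | 54.0 | 48.6 | 43.7 |
| 20% | 48.0 | 38.4 | 30.7 |

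The 2-month count is the same either way.

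**5. Power at 4 months.** Use Φ(d·√(n₁n₂/(n₁+n₂)) − 1.96), with assumed d = 0.5, two-sided 5% (the plan states no sidedness), and the delayed arm at 60(1 − m). For m = 10% without the rule: 0.5 × √(54 × 54 / 108) = 2.598, power 0.738. With it: 0.5 × √(48.6 × 54 / 102.6) = 2.529, power 0.715. For m = 5% the pair is 0.761 and 0.750; for m = 20% it is 0.688 and 0.637.

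**The case against.** The best defence is that the rule has real safeguards. A caregiver who misses an interview but is reached is not lost. The label follows only after four weeks of rescheduling attempts, calls and, if needed, a letter. That stands, and it should keep the affected number small. It does not supply a provision for later visits once the label is given.

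Four stronger readings are tempting, and the documents do not support them.

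- *That later visits are discarded.* The protocol says neither that remaining interviews are cancelled nor that data already collected are dropped; section 10 keeps all available data. Not approaching someone recorded as withdrawn is the ordinary consequence, but it is an inference.
- *That the protocol has an arm-specific rule.* It has none. The section speaks of caregivers generally and covers Aims 2 and 3, and its singular follow-up also fits the single post-program contact of Aim 2. The asymmetry comes from the literal wording. On the 3/6-month schedule in section 5, a delayed-arm caregiver who misses the first post-program interview faces the same loss, so over the whole study the arms are alike there.
- *That the primary contrast is undermined.* A missed 2-month interview is already missing when the label is applied.
- *That bias is shown.* Nothing documents that unreachable caregivers are the more burdened ones, and section 10 plans to include predictors of missingness as covariates. Lost later interviews cost precision; added bias is possible, but not demonstrated.

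It is also fair to say that the conflict between the two schedules lies underneath this problem, because the number of visits at risk depends on it.

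**Conclusion.** The point holds as a cheap improvement. The withdrawal rule is explicit, there is no provision for later interviews, and on both schedules the label comes before the next one. That works against the reason given for choosing mixed models. Within the 4-month wait, the literal wording covers the immediate arm only.

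The main exposure is the later longitudinal and sustained-effect analyses. The primary contrast is exposed only through unequal tracing effort at 2 months.

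The size is modest: 5–15% of the immediate arm's later interviews under the assumed unreachability rates and 60 per arm. The illustrative 4-month power loss is 0.011 at m = 5%, 0.023 at 10% and 0.051 at 20%, and rests on the further assumptions of d = 0.5 and independence between visits. Avoidable imbalance in follow-up is a better reason to act than power.

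**What to change.** Reword Lost to Follow Up as follows.

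1. Record an unreachable visit as missing for that visit only, separately from withdrawal.
2. Attempt every later scheduled interview in both arms unless the caregiver withdraws consent.
3. Apply the same tracing steps and window to every scheduled interview, including the delayed arm's pre-program ones.
4. Assign lost-to-follow-up status only after the final scheduled interview. This also removes a circularity: contact attempts are now listed both as actions once a participant is judged lost and as steps before that judgement.
5. Reconcile the 2/4/6-month and 3/6-month schedules across section 5, Recruitment, Field Methods and section 10, so that the visits covered are clear.

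The cost is protocol wording, a few extra calls and the $25 gift card for each interview obtained: at most 18 × $25 = $450 for the immediate arm at the top of the range above. The change helps only interviews still to come, since those not attempted cannot be recovered afterwards.
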